6.5.5 Pregnancies

A detailed listing of all pregnancies will be provided if any occur using All Screened Set.

6.5.6 Other Safety-Related Assessments

6.5.6.1 Post Void Residual Volume

PVR will be summarized, for each age group and overall, by treatment group and visit using mean, standard deviation, median, minimum, and maximum at each treatment visit, including changes from baseline. In case of 2 measurements at the same visit, the lowest (instead of mean) PVR volume will be used for the calculations.

Summary of PVR data will be presented for visits 3, 5, 7 and 8 (EoS), and for EoT values.

To calibrate PVR with bladder size, the ratio of PVR to the child's Expected Bladder Capacity (EBC, =[age+1] \times 30 in mL for children and 400 mL for adolescents) will also be

calculated at baseline and post-baseline study visits and expressed as a percentage. These ratios will be summarized together with the change from baseline by age group and overall.

The following variables will be summarized, for each age group and overall, by treatment group at each visit (and also for the maximum recorded post-baseline value of PVR) using number and percentage of subjects in the following categories:

- PVR: 0 to <20 mL, 20 to <50 mL, ≥50 mL
- Change from baseline in PVR: <0 mL, 0 to <20 mL, 20 to <50 mL, ≥50 mL
- Ratio of PVR to EBC (%): 0% to <20%, 20% to <40%, ≥40%
- Change from baseline in ratio of PVR to EBC (%): <0%, 0% to <20%, 20% to <40%, ≥40%

PVR data will be provided in listing format by country, site and subject for the SAF.

6.5.6.2 Body Weight and Height

Body weight, height and BMI will be summarized, for each age group and overall, by treatment group and visit using mean, standard deviation, median, minimum, and maximum at each visit, including changes from baseline. Summary of body weight, height and BMI will be presented for visits 1, 3 and 7, and for EoT values.

Body weight, height and BMI data will be provided in listing format by country, site and subject for the SAF.

6.5.6.3 Acceptability and Palatability Questionnaires

Results from the acceptability and palatability questionnaire for tablets (see protocol Section 12.8) and for oral suspension (see protocol Section 12.9) will be summarized at week 12/EoT, for each age group and overall, by treatment group.

Data obtained from the questionnaires will be provided in listing format by country, site and subject for the SAF.

6.5.7 Subgroups of Interest for Safety

In addition to the analyses described above, selected safety variables (TEAEs, drug-related TEAEs and Vital Signs) will be summarized for each age group and overall by treatment group for several subgroups.

For TEAEs and drug-related TEAEs the subgroups are: sex, race, ethnicity, geographical region, formulation (tablets vs. oral suspension), prior OAB treatment and symptomatic UTI, and for vital signs: sex, race, ethnicity, and formulation (tablets vs. oral suspension). For any of the subgroups specified for vital signs, at least 10 subjects by stratum are required.

6.6 Analysis of Pharmacokinetics

Plasma concentrations for mirabegron will be sampled at visit 5/week 4 and visit 7/week 12 (EoT) (Table 9). One predose sample will be collected on both pharmacokinetic sampling days. On pharmacokinetic sampling days, dosing should occur in the clinic and breakfast should be eaten at the clinic within 1 hour before dosing.

Visit	t Time Point Collection Window		Whole Blood Pharmacokinetics
Visit 5/week 4	Predose (trough)	Approximately 24 hours after previous dose	Х
Visit 7/week 12 (EoT)	Predose (trough)	Approximately 24 hours after previous dose	Х

Table 9	Sample Collectio	n Schedule

EoT: end of treatment

Pharmacokinetic analysis will be conducted on the PKAS and conducted separately for children, adolescents and overall. Descriptive statistics (n, mean, SD, minimum, median, maximum, coefficient of variation (CV), geometric mean and geometric CV) will be used to summarize plasma concentrations of mirabegron by visit. Plasma concentration values below the lower limit of quantification (LLOQ, 0.0500 ng/mL) will be set equal to 0 in the calculation of summary statistics.

The following plot will be produced: Box plots of plasma concentration-time profiles (normal scale and semi-log scale).

Further details will be described in the TLF specifications.

Pharmacokinetic analysis will be conducted on the PKAS and parameters will be summarized for children, adolescents, and overall in the modeling report. Results of the pharmacokinetic analysis will be provided in a separate PK modeling report.

6.6.1 Statistical Analysis

Plasma concentration data from this study will be pooled with other pediatric PK data and will be analyzed using a population modeling approach. Details of the pharmacokinetic analysis will be presented in a separate population PK modeling analysis plan.

6.7 Analysis of Pharmacodynamics

Not applicable.

6.8 Other Analyses

Not applicable.

6.9 Interim Analysis (and Early Discontinuation of the Clinical Study)

One comparative interim analysis will be performed after 50% of children planned to be randomized have had their week 12/EoT assessment. Only data from those children with week 12/EoT assessment will be used in the interim analyses. The interim analysis will determine if the chance of a positive study with respect to the primary endpoint at the final analysis is high enough to justify continuation of the study; otherwise, the study will be stopped for futility.

Given the data at the interim analysis, a predictive probability of a positive study will be calculated. A positive study is defined as the final 1-sided p-value ≤ 0.05 when comparing mirabegron vs. placebo in the primary efficacy analysis (in children [5 to < 12 years of age]).

If the predictive probability is $\leq 5\%$ at this interim evaluation, the study will be recommended to stop for futility. Otherwise, the study will continue.

No efficacy analyses will be performed except for determination of futility.

At the interim analysis, the following predictive probability will be calculated: Predictive Probability of ({final one-sided p-value of mirabegron vs. placebo ≤ 0.05 } |Data).

Since we use non-informative prior distribution of difference in mean change from Baseline to week 12/EoT in mean number of micturitions per 24 hours between the mirabegron group and the placebo group and assume the mean change from Baseline to week 12/EoT in mean number of micturitions per 24 hours follows a Gaussian distribution, the Bayesian predictive probability for the event of a final one-sided p-value of mirabegron vs. placebo ≤ 0.05 (denoted by *PP*) can be obtained using a closed form based on the methods described in Geisser and Johnson (1994), Spiegelhalter etc. (2004), Dmitrienko and Wang (2006). Appendix 9.5 contains a detailed derivation.

$$PP = \Phi \left\{ \sqrt{\frac{2}{\frac{M_P}{N_P} + \frac{M_A}{N_A}}} \left[\sqrt{82} \frac{\overline{y}_{N_P} - \overline{x}_{N_A}}{\sqrt{2}\hat{\sigma}} - z_{0.95} \right] \right\}$$
(1)

where

- Φ stands for the cumulative distribution function for the standard Gaussian distribution. $\Phi(Z_{0.95}) = 0.95$.
- N_P and N_A denote the number of subjects observed at the interim analysis for placebo group and mirabegron group, respectively.
- M_P and M_A denote the number of subjects as yet unobserved at the interim analysis for placebo group and mirabegron, respectively. $M_P = 82 - N_P$, $M_A = 82 - N_A$.
- \bar{y}_{N_P} and \bar{x}_{N_A} are the LS means for placebo group and mirabegron group, respectively, and will be obtained from the ANCOVA model described in Section 6.4.1.1.
- $\hat{\sigma}$ is the estimated pooled standard deviation and will be obtained from the same ANCOVA model as described in Section 6.4.1.1.

Detailed information on the decision rule for futility and simulations illustrating the operational characteristics of such futility criteria can be found in Appendix 9.4.

The interim analysis will be conducted by an Independent Data Analysis Center (IDAC). An independent statistician at this IDAC will be unblinded to conduct the interim analysis.

Documentation of the interim analysis will be kept at the IDAC until after end of study treatment unblinding, and will then be transferred to the Study TMF.

The recommendation from the IDAC (to stop the study for futility or continue as planned) will be forwarded to the Therapeutic Area Head Medical Specialties, to act upon this

recommendation (see Appendix 9.6: Interim Analysis Report Template). His decision to stop or continue the study will be communicated to the study manager.

6.9.1 Data Sources

There are 2 databases: the IRT database provided by Cenduit and the clinical database. The IRT database will include all randomization and study drug supply data collected through IRT. The clinical database for the study is based on electronic data capture (EDC) technology. All clinical data should be captured electronically in the clinical database after the corresponding visits.

The unblinded randomization data and study drug supply data will only be located in the IRT database prior to the final database lock. The unblinded randomization data and study drug supply data will be transferred to the IDAC directly from the IRT database or IRT vendor for generating the Report. This process will maintain the confidentiality of the treatment codes by having only the IDAC statistician access the IRT independently of any Astellas personnel (e.g., clinical supply). This process will be documented by IRT vendor SOPs.

6.9.2 Data Cut-off and Data Extraction

The data cut-off date will be the target date for priority data cleaning. Data collected prior to data cut-off date will undergo standard data review and cleaning procedures by Signant Health and APGD Data Management. When priority data cleaning is deemed sufficient, the database will be extracted in SAS data format. All relevant (efficacy, disposition, study medication and demographic) data collected in the clinical database prior to the data extraction date will be included in the report.

6.9.3 Report Generation

The IDAC will develop analysis programs based on surrogate treatment codes prior to the cut-off date. The unblinded IDAC statistician that is not affiliated with APGD will receive the unblinded randomization data from the IRT. The IDAC statistician will replace surrogate treatment codes with actual treatment codes and generate outputs using the programs developed by the IDAC.

The IDAC statistician will prepare a statistical report, being the Interim Analysis Report (Appendix 9.6) and the TFL (Table, figure and listing) outputs, see below, for the Therapeutical Area Head Medical Specialties.

Table Number	Table Title		
1.1	Disposition Prior to Randomization, All Subjects With Informed Consent		
1.2	1.2 Subject Classification, All Randomized Subjects		
1.3	Subject Enrollment, Overall and by Country/Site, All Randomized Subjects		
2	2 Demographics, Full Analysis Set		
3	Results of ANCOVA of Change from Baseline in Mean Number of		
	Micturitions per 24 hours at Week 12/EoT, Full Analysis Set		

For the interim report the following tables will be presented:

Note: no safety data will be presented

Table 10

6.10 Additional Conventions

6.10.1 Analysis Windows

The study protocol gives the overall study schedule and the permissible intervals for these visits expressed as the number of days relative to visit 3/baseline. The total time each subject will be in the study will not exceed 18 weeks with a maximum of a screening period of 4 weeks and a maximum of 14 weeks for the investigational period.

Analyses will not exclude subject data due to the subject's failure to comply with the visit schedule.

Visit Windows for Efficacy and Safety Parameters

CRF visit	Target day relative to Baseline (Visit 3, Day -1)	Analysis Window	Analysis visit
Bladder e-d	liary		
Visit 3	Last value prior to first dose	Day -7 to Day 1 (prior to first dose)	Baseline
Visit 4	Day 14	Day 7 to Day 21	Week 2
Visit 5	Day 28	Day 22 to Day 42	Week 4
Visit 6	Day 56	Day 43 to Day 70	Week 8
Visit 7	Day 84	Day 71 to Day 91	Week 12
ЕоТ	Day 84	Day 1 to \leq Last dose of double- blind study drug	ЕоТ
Acceptabili	ty questionnaires		
Visit 7	Day 84	Day 71 to Day 91	Week 12
ЕоТ	Day 84	Day 1 to \leq Last dose of double- blind study drug	ЕоТ
SBPM			
Visit 3	Last value prior to first dose	Day -7 to Day 1 (prior to first dose)	Baseline
Visit 4	Day 14	Day 7 to Day 21	Week 2
Visit 5	Day 28	Day 22 to Day 42	Week 4
Visit 6	Day 56	Day 43 to Day 70	Week 8
Visit 7	Day 84	Day 71 to Day 91	Week 12
ЕоТ	Day 84	Day 1 to \leq Last dose of double- blind study drug	ЕоТ
Table contin	nued on next page		

All the assessments will be allocated to CRF visit based on Table 10.

CRF visit	Target day relative to Baseline (Visit 3, Day -1)	Analysis Window	Analysis visit	
Vital signs				
Visit 1			Screening	
Visit 3	Last value prior to first dose	Day -7 to Day 1 (prior to first dose)	Baseline	
Visit 5	Day 28	Day 22 to Day 56	Week 4	
Visit 7	Day 84	Day 57 to Day 91	Week 12	
ЕоТ	Day 84	Day 1 to \leq Last dose of double- blind study drug	ЕоТ	
Visit 8 [#]	Day 98	Day 92 or EoT + 1 to no more than 17 days after EoT	Week 14 (EoS)	
ECG	-			
Visit 1			Screening	
Visit 3	Last value prior to first dose	Day -7 to Day 1 (prior to first dose)	Baseline	
Visit 5	Day 28	Day 22 to Day 56	Week 4	
Visit 7	Day 84	Day 57 to Day 91	Week 12	
ЕоТ	Day 84	Day 1 to \leq Last dose of double- blind study drug	ЕоТ	
Clinical Lab	ooratory Tests (Hematology, B	iochemistry and Urinalysis)		
Visit 1			Screening	
Visit 3	Last value prior to first dose	Day -7 to Day 1 (prior to first dose)	Baseline	
Visit 5	Day 28	Day 22 to Day 56	Week 4	
Visit 7	Day 84	Day 57 to Day 91	Week 12	
ЕоТ	Day 84	Day 1 to \leq Last dose of double- blind study drug	ЕоТ	
Visit 8 [#]	Day 98	Day 92 or EoT to no more than 17 days after EoT	Week 14 (EoS)	
Post Void Residual (PVR) Volume				
Visit 3	Last value prior to first dose	Day -7 to Day 1 (prior to first dose)	Baseline	
Visit 5	Day 28	Day 22 to Day 56	Week 4	
Visit 7	Day 84	Day 57 to Day 91	Week 12	
ЕоТ	Day 84	Day 1 to \leq Last dose of double- blind study drug	ЕоТ	
Visit 8 [#]	Day 98	Day 92 or EoT to no more than 17 days after EoT	Week 14 (EoS)	

[#]Visit 8 may occur earlier due to early discontinuation as it is the last scheduled study visit.

For non-diary data, if a subject has more than one non-missing value within a visit window, the non-missing assessment which is closest to the target day within a window will be used. If two or more values are equally close and on different days, the latest non-missing value will be used. If two or more values are equally close and on the same day, the mean will be used for continuous variables or the worst observed case for categorical variables.

For diary data, the assessment date for the whole diary will be considered to be the date of the last valid day of the diary. If more than one diary has an assessment date within the same window, and if this results in more than one non-missing value of a diary variable, the non-missing value with the diary assessment day that is closest to the target day will be used. In case of ties on different days, the later non-missing value will be used. In case of ties located on the same side of the target day (i.e., more than one value for the same day), the mean of the values will be used for continuous variables and the worst value for categorical variables. For analyzing diary data the labels of the study visits will not be used, they will be assigned based on the dates of assessment.

A two-day window around the visit date will be applied for the assignment of study period for exposure data.

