| | Day -28 | Day -14 | Day -1 | Day 14 | Day 28 | Day 56 | Day 84 | Day 98 |
| | (-3 days) | (± 5 days) | | (± 3 days) | (± 3 days) | (± 3 days) | (± 3 days) | (+ 3 days) |
| Acceptability and Palatability Questionnaire ^m | | | | | | | X | |
| Pharmacokinetics ⁿ | | | | | X | | X | |

AE: adverse event; ECG: electrocardiogram; e-diary: electronic diary; EoS: end of study; EoT: end of treatment; IP: investigational product; PED25: pediatric equivalent dose 25 mg; PED50: pediatric equivalent dose 50 mg; PVR: post void residual; SBPM: self blood pressure monitoring; TC: telephone call

- a. For the visits where a TC is indicated, there is no need for the subject to visit the clinic provided that the bladder e-diary data are reviewed by the investigator prior to the TC and discussed and confirmed with the subject or parent(s)/legal guardian(s) during the TC. Urotherapy is also to be discussed and confirmed with the subject or parent(s)/legal guardian(s) during each TC.
- b. Subjects who withdraw early from the study after having received IP should complete both the EoT and EoS visits.
- c. The EoS visit (visit 8/week 14 [EoS]) should take place at least 14 days after the EoT visit (visit 7/week 12 [EoT]).
- d. Subjects using prohibited medication will complete 1 week of washout (if applicable), while beginning 4 weeks of urotherapy.
- e. Dose up-titration to PED50 to occur at visit 5/week 4 unless investigator determines OAB is adequately controlled. Dose down-titration from PED50 to PED25 can be done at any time for safety reasons.
- f. Daily IP administration will start on day 1 (i.e., the day after visit 3/week 0 [baseline]).
- g. Blood pressure, pulse, body temperature and ECGs will all be measured in single measurements. Subject to be in the sitting position (when possible, otherwise supine, but always in the same position for each procedure). Subject should have been calm and without distress for at least 5 minutes. Preferably, the right arm should be used to measure vital signs. Body temperature will be measured with an ear thermometer. Clinic measurements will be used to assess eligibility.

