5.5 Other Endpoints

5.5.1 Exposure to Study Drug

The duration of exposure to each dose of study drug (PED25 and PED50) by visit and for the whole period will be calculated using the following information that is recorded in the eCRF:

• Overall start date and stop date of the study medication.

The first dose of study drug is to be administered on Day 1, the day after the baseline visit (visit 3). The initial dose will be PED25 for all subjects. The last dose of treatment is to be taken in the morning of visit 7/week 12/EoT.

• Start date and new dose of study drug at each titration step.

At visit 5/week 4 the dose may be up-titrated, or may remain the same. Dose down-titration from PED50 to PED25 can be done at any time thereafter for safety reasons.

- Start date and new dose of study drug after each unscheduled dose change.
- At any time during the treatment period, the subject may have an unscheduled dose interruption or reduction. At each unscheduled change in dose, the (new) dose, start date and reason are recorded.

In addition, the return date of study medication is assumed to be the date of clinical visit.

In all cases where there is a dose change, either because of dose titration or an unscheduled dose interruption, reduction or increase, the last dose of the medication at the old level will be assumed to be the day before the given date of first dose at the new level. In this way, the subject's dosing history can be reduced to a series of unbroken intervals within each of which, the dose level is constant. From these, the subject's exposure at each dose can be calculated.

To illustrate, consider a subject with the following dose information on the eCRF:

- The dates of the very first and very last dose of the study medication given at D1=1st July 2019, Dlast=24th September 2019.
- Up-titration to PED50 at Visit 5. The first dose at the new level is given at D2=29th July 2019.
- Study drug interrupted at an unscheduled visit. The date of last dose at the PED50 level is given at D3=1st August 2019.
- Study drug re-started at PED25 at an unscheduled visit. The first dose at the new level is given at D4=5th August 2019.
- Remains at PED25 till Visit 6 (D5=25th August 2019). Up-titration to PED50 at Visit 6. First dose at the new level is given at D6=26thAugust 2019.

From these dates we calculate the following:

- The duration of exposure to the treatment can be calculated as ETOT=Dlast-D1+1-(D4-D3-1) =83 days.

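### SAP Table 10 closes the Week 14 (EoS) window 17 days after EoT although the protocol's visit windows allow 20, and its laboratory and PVR rows open on the EoT day itself

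*SAP*

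**What the plan says.** SAP section 6.10.1 gives the rule "All the assessments will be allocated to CRF visit based on Table 10". For Week 14 (EoS), the vital signs row of that table reads "Day 92 or EoT + 1 to no more than 17 days after EoT". The laboratory and PVR rows read "Day 92 or EoT to no more than 17 days after EoT". For the same three measures the Week 12 window is "Day 57 to Day 91", and the EoT window stops at the last dose.

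The protocol's Schedule of Assessments (section 1.3, Table 1) places visit 7 on Day 84 with a tolerance of 3 days either way, and visit 8 on Day 98 with a tolerance of 3 days later only. Footnote c adds that the EoS visit "should take place at least 14 days after the EoT visit". It gives a minimum and no maximum.

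Three other SAP statements bear on the point:

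- Section 6.10.1 says the protocol gives "permissible intervals for these visits expressed as the number of days relative to visit 3/baseline".
- The same section says: "Analyses will not exclude subject data due to the subject's failure to comply with the visit schedule".
- Section 5.5.1 says: "The last dose of treatment is to be taken in the morning of visit 7/week 12/EoT". For a child who completes treatment, the last-dose date and the visit 7 date therefore coincide.

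Vital signs and PVR are scheduled at visit 8 for everyone. Visit 8 laboratory tests are done only after a relevant adverse event or at the investigator's discretion (protocol Table 1, footnote i).

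**The concern.** An analysis window should accept every assessment that the protocol's own visit windows permit. Here the upper limit is counted from EoT, while the protocol tolerances are counted from baseline, and the two do not give the same longest interval. A child can attend both visits on time and still have visit 8 values with no analysis visit. The SAP undertakes not to exclude data even when the schedule is missed, so leaving out compliant data is inconsistent with its own principle.

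The lower limit has a different problem. Starting the laboratory and PVR rows on the EoT day lets a value taken on the last day of dosing into a column meant to describe children off drug.

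For children who complete treatment, visit 8 is the only scheduled off-drug clinic measurement of blood pressure, pulse and PVR. Increased blood pressure, increased heart rate and urinary retention are among the identified risks in protocol section 2.1.3. The SAP plans visit 8 summaries of laboratory tests (6.5.2), clinic vital signs (6.5.3.1) and PVR (6.5.6.1). Those summaries are what is at stake.

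**Working it through.** **Inputs.** Visit 7: Day 84 ± 3, that is Days 81 to 87. Visit 8: Day 98 + 3, that is Days 98 to 101. Minimum gap: 14 days. All are from protocol Table 1 and footnote c. SAP limit: 17 days after EoT. For completers EoT is taken as the visit 7 date (SAP 5.5.1).

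**Where 17 comes from.** It can be reproduced in two ways: (98 + 3) - 84 = 17, which assumes visit 7 falls exactly on Day 84; or 14 + 3 = 17, which assumes the three-day tolerance runs from EoT.

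**Longest compliant gap.** Latest visit 8 minus earliest visit 7 = (98 + 3) - (84 - 3) = 101 - 81 = 20 days.

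**All compliant day pairs** (visit 8 on Days 98-101 and at least 14 days after visit 7):

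| Visit 7 | Compliant visit 8 days | Gaps (days) | Pairs | Pairs over 17 days |
|---|---|---|---|---|
| Day 81 | 98-101 | 17-20 | 4 | 3 (Days 99, 100, 101) |
| Day 82 | 98-101 | 16-19 | 4 | 2 (Days 100, 101) |
| Day 83 | 98-101 | 15-18 | 4 | 1 (Day 101) |
| Day 84 | 98-101 | 14-17 | 4 | 0 |
| Day 85 | 99-101 | 14-16 | 3 | 0 |
| Day 86 | 100-101 | 14-15 | 2 | 0 |
| Day 87 | 101 | 14 | 1 | 0 |
| Total | | 14-20 | 22 | 6 |

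**Does another window take the six?** Their visit 8 days are 99, 100 and 101. The Week 12 window ends on Day 91 and the EoT window ends at the last dose, so the answer is no for all six.

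**Lower limit.** Take as an illustration a child whose last dose and EoT assessments both fall on Day 28, the visit 5 target day. Read literally, the laboratory row for Week 14 runs from Day 28 to Day 28 + 17 = Day 45. Visit 8 is due no earlier than Day 28 + 14 = Day 42. If no conditional laboratory test is done then, the Day 28 sample is the only value in the window and becomes the Week 14 result. Under the vital signs wording the window would start on Day 29 and this could not happen. For PVR, which is scheduled at visit 8, the rule of choosing the value closest to the Day 98 target would select an in-window visit 8 value. The problem arises there only if no such value exists.

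**The case against.** The strongest reply is that 17 is simply 14 + 3. Footnote c ties visit 8 to the EoT visit, the follow-up period is described as two weeks, and a later-only tolerance suits a minimum interval. If the three days were meant to run from EoT + 14, the longest gap is 17 days and the SAP agrees with the protocol. That may have been the intention, but it is not written. Table 1 attaches the tolerance to Day 98, the SAP describes the intervals as relative to baseline, and footnote c sets no upper limit.

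Other parts of the defence do stand:

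- **Size.** A visit 8 on its Day 98 target is never lost, because 98 - 81 = 17. Loss needs an early visit 7 together with a late visit 8. A reader might infer that 6/22 (27%) of visit 8 assessments are lost, or 21% by spreading visits evenly over their allowed days, (3/4 + 2/4 + 1/4)/7. The documents give no distribution of visit timing, so neither figure is an estimate.
- **Data kept.** A reader might infer that the values are discarded. They remain in the listings, and the SAP also summarises the maximum post-baseline PVR, which does not depend on the Week 14 window. No test of reversal after stopping is planned.
- **Early stoppers and the 17-day limit.** A reader might infer that anyone whose EoT visit is four or more days after the last dose is cut off, since 4 + 14 = 18. That holds only if the 17 days are counted from the last dose. Table 10's EoT row sets an interval for choosing EoT values; it does not say which date the Week 14 limit is counted from.

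**Conclusion.** The mismatch stands as a defect in the descriptive safety analysis. On the windows as written, the longest compliant interval from EoT to visit 8 is 20 days and Table 10 stops at 17. Six of 22 compliant day pairs therefore have no analysis visit. The consequence is confined to the Week 14 summaries, and it is nil if every visit 7 falls on or after Day 84. The different starting points of the rows are a second, narrower fault: they matter mainly for laboratory results of early stoppers with no visit 8 test.

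This rests on reading the protocol tolerances from baseline, as the SAP does, and, for completers, on EoT being the visit 7 date. The on-drug laboratory case further assumes that the EoT sample was taken on the last-dose day. The primary efficacy analysis is not affected.

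**What to change.** Amend the Week 14 (EoS) entry in Table 10 identically for vital signs, laboratory tests and PVR:

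1. Extend the upper limit to at least 20 days after EoT.
2. Start at EoT + 1 in every row.
3. State whether EoT here means the last-dose date or the date of the EoT visit.
4. Keep the Day 92 start for children who complete treatment, and say that the EoT + 1 start applies to early stoppers.

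The Day 92 start should not be dropped. Without it, a completer with a last dose on Day 81 would have Days 82-91 in both the Week 12 and Week 14 windows. Removing the upper limit altogether would likewise let later off-drug values of early stoppers compete for two analysis visits.

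The cost is a small edit to Table 10 and to the windowing program before hard lock, which SAP section 1 permits. A few off-drug values taken up to three days later than now allowed (20 - 17) would enter the Week 14 summaries.
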